4.7.3.1. Cohort Progression/Escalation and Suspension/Stopping Rules in Part A

Study cohort progression/escalation and suspension/stopping rules for AEs considered possibly or definitely related to study drug for Part A are described in [Table 6](#). If a subject meets a stopping rule, the subject will be managed as clinically indicated and asked to complete all safety assessments according to the protocol.

Table 6: Cohort Progression/Escalation and Suspension/Stopping Rules for Part A

CTCAE Grade ^a	Severity/Seriousness	Reversibility	Number of Subjects Affected	Action	Effect on Dose Progression/Escalation
I	Mild	N/A	N/A		
II	Moderate	Showing signs of reversibility (ie, AE which shows signs of improvement in the judgment of Investigator)	≤2 subjects in different SOC	Next dose determined by SRC	N/A
			≤2 subjects in same SOC OR 3 subjects in different SOC ^b	Dose level may continue OR be extended AND dose escalation on hold until results of continuation or extension are available	Following continuation or extension, dose escalation may proceed as per clinical study protocol
			≥3 subjects in same SOC OR ≥4 subjects in different SOC ^b	Dose level suspended	A lower (intermediate) dose level may be administered in the next cohort AND dose continuation, extension, or escalation requires Regulatory Agency, IEC/IRB, and SRC approval
		Showing no signs of reversibility	≥2 subjects ^b		

Table 6: Cohort Progression/Escalation and Suspension/Stopping Rules for Part A

CTCAE Grade ^a	Severity/Seriousness	Reversibility	Number of Subjects Affected	Action	Effect on Dose Progression/Escalation
III	Severe, not serious	Showing signs of reversibility (ie, AE which shows signs of improvement in the judgment of Investigator)	1 subject ^b	Dose level may continue OR be extended AND dose escalation on-hold until results of continuation or extension are available	Following continuation or expansion, dose escalation may proceed as per the clinical study protocol
			≥2 subjects ^b	Dose level suspended	A lower (intermediate) dose level may be administered in the next cohort AND dose continuation, extension or escalation requires Regulatory Agency, IEC/IRB, and SRC approval
	Showing no signs of reversibility	≥1 subject			
	Severe, serious	N/A			
IV/V	Life-threatening/ Fatal	N/A	≥1 subject	Study suspended	Study continuation requires Regulatory Agency, IEC/IRB, and SRC approval

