D. Optional Cohorts	1. Optional cohorts may be included to explore additional dosing regimens	
I. Up to 2 optional cohorts may be included in Part A.
 
II. Up to 3 optional cohorts may be included in Part B.
 
III. Cohort sizes will not exceed 8 subjects for each optional cohort in Part A, and 8 patients for each optional cohort in Part B.
 
IV. To further explore safety, tolerability, PD, and/or PK, study drug dose level may be escalated or de-escalated to a lower and/or to intermediate dose levels. Dose escalation in Part B will not exceed a dose level found to be safe and well-tolerated in Part A.
 
V. Dosing in optional cohorts will follow the same randomization list as that in planned cohorts in the respective parts of the study.
 
VI. The total number of study subjects/patients indicated in Section 4.3 cannot be exceeded.

E. Samples and assessments	1. If applicable, the inpatient period may be prolonged for subjects/patients in all dose levels in all cohorts if considered by the Investigator to be necessary for clinical reasons or for expeditious	
I. If applicable, a maximum extended inpatient period due to clinical concerns cannot be defined as the extension will be as long as necessary to ensure the safety of the subjects/patients.
 
II. If applicable, an unplanned or extended inpatient stay because of a suspected adverse

Table 9: Adaptive Study Design Areas, Features, and Limits

Areas	Features	Limits
	conduct of the study. Prolonged inpatient periods will be recommended on a subject/patient, case-by-case basis and/or if the SRC considers it necessary for determining safety and tolerability for a future dose level cohort.	event will constitute a serious adverse event and will be considered in the context of the study stopping rules (Section 4.7).
	2. Specialist referrals may be made if considered clinically necessary by the Investigator, delegate, Sponsor, or SRC for subjects/patients on a case-by-case basis.	I. Specialist referrals for subjects/patients will be determined on a case-by-case basis, as necessary to ensure the safety of subjects/patients, so a maximum number of referrals cannot be defined.

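### Part A stopping rules use seriousness only at Grade III, so one related Grade II SAE does not suspend a dose level, although it would suspend a Part B cohort

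*Protocol*

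**What the plan says.** Table 6 in Protocol Section 4.7.3.1 covers Part A adverse events judged possibly or definitely related to study drug. Grade II is labelled as moderate and nothing more. It is divided by reversibility and by number of subjects:

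- Reversible, up to two subjects in different system organ classes (SOCs): "Next dose determined by SRC".
- Reversible, up to two subjects in one SOC or three in different SOCs: "Dose level may continue OR be extended AND dose escalation on hold until results of continuation or extension are available".
- Reversible, "≥3 subjects in same SOC OR ≥4 subjects in different SOC": the dose level is suspended.
- "Showing no signs of reversibility": the only count given is two or more subjects, and the dose level is suspended.

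For a suspended level, the effect column adds that "dose continuation, extension, or escalation requires Regulatory Agency, IEC/IRB, and SRC approval".

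At Grade III the table does separate serious from non-serious events. One reversible non-serious case only holds escalation; one serious case suspends the level. At Grade IV or V a single case suspends the study.

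Three other places bear on this:

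- Section 7.5.7.1 treats severity and seriousness as separate judgements.
- Table 9 (Section 4.8, area E, limit II) provides that an unplanned or extended inpatient stay on account of a suspected adverse "event will constitute a serious adverse event and will be considered in the context of the study stopping rules (Section 4.7"). No grade condition is attached.
- Table 8 (Section 4.7.3.3) suspends dosing in a Part B cohort, and in any higher-dose cohort, when one patient has a related severe event or a related SAE of whatever grade. The SRC reviews the case and may then allow the cohort to continue.

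**The concern.** Table 9 sends a class of SAEs to the Section 4.7 stopping rules without regard to grade, but below Grade III the Part A table has no entry that uses seriousness. A related Grade II SAE in a healthy volunteer is therefore handled as any other moderate event. The written rule then either leaves a choice between two non-suspending actions or gives no action at all. The same event in a patient stops dosing of the cohort until the SRC has looked at it.

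At stake is whether the other subjects at that level may still be dosed under the written rule after a related SAE. Section 4.6 names Table 6 as the source of the criteria for stopping cohorts, so a gap there is a gap in the operative rule. Healthy volunteers have no benefit to set against the risk (Section 1.5).

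**Working it through.** The plan states no error rate or operating characteristic for these rules, so there is no figure of its own to reproduce. The check is a row-by-row reading with simple counts.

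**Inputs.** A Part A cohort has 8 subjects randomized 3:1 (Section 4.1.1), so 8 × 3/4 = 6 are active. A Part B cohort has 4 patients (Section 4.1.2). Thresholds are those of Tables 6 and 8. Part A may have up to 2 optional cohorts (Section 4.7.1).

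**Step 1. One related Grade II SAE (k = 1) against each rule.**

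| Rule | Condition | Met at k = 1? | Suspends? |
|---|---|---|---|
| Table 6, reversible, first row | k ≤ 2, different SOCs | yes | no |
| Table 6, reversible, second row | k ≤ 2, same SOC | yes | no |
| Table 6, reversible, third row | k ≥ 3 same SOC, or k ≥ 4 different | no | – |
| Table 6, not reversible | k ≥ 2 | no | – |
| Table 8, Part B cohort | k ≥ 1 related SAE | yes | yes |

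A single subject can be read into either of the first two rows, and their actions differ. A reversible case thus matches 2 rows and a non-reversible case 0, with 0 suspensions either way. Table 6 has merged cells, but no assignment of them yields a seriousness entry at Grade II or a one-subject entry for non-reversible events.

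**Step 2. Number needed to suspend.**

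- Part A, not reversible: 2/8 = 25%
- Part A, reversible, same SOC: 3/8 = 37.5%
- Part A, reversible, different SOCs: 4/8 = 50%
- Part B, related SAE: 1/4 = 25%

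**Step 3. Can a Grade II SAE arise?** Set the SAE criteria in Section 7.5.7.1 beside its grade descriptions. Death corresponds to Grade V and a threat to life to Grade IV. Hospitalization or its prolongation, disability, and medically important events all have counterparts in the Grade III wording. Only congenital anomaly has none. Most SAEs should therefore be graded III or higher. The grade text is, however, a general guide that defers to CTCAE for each event, and Table 9 makes a stay for a suspected event an SAE whatever its grade. Part A subjects are already resident from Day -1 to Day 2, so a moderate event that prolongs the stay is a possible route. The documents give no example and no frequency.

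**Step 4. Reach.** Part A data had already fixed the Part B starting dose (Sections 1.4 and 4.7.2). Taking the three planned cohorts as dosed, what remains is at most 2 × 8 = 16 subjects, 2 × 6 = 12 of them active, and 0 if no optional cohort is opened. No within-cohort stagger is stated, so between 0 and 8 − 1 = 7 other subjects could still be dosed after the event.

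**The case against.** The strongest reply is that the protocol's own grading almost removes the case. Step 3 shows that this is largely right, and it is why the point is minor. It does not close the gap, because separate assessment of severity and seriousness leaves a Grade II SAE possible.

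A second reply is that the two parts differ by design: one dose in healthy adults at one center, against repeated doses in patients from age 6 in smaller cohorts. Different thresholds are not in themselves an inconsistency, and the non-reversible threshold is the same share of a cohort (25%). This stands. What it does not explain is why seriousness counts at Grade III in Part A but not at Grade II, or why one non-reversible case has no row.

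A reader might infer that dosing would carry on unreviewed. The documents do not support that. SAEs go to the sponsor within 24 hours; the investigators, SRC and sponsor are unblinded. The SRC reviews at least 48 hours of data from at least 6 subjects before escalation, may change the Part A dose, and may recommend stopping the study. None of these is a stated suspension criterion, and the scheduled Part A review precedes escalation, not the dosing of the remaining subjects in the same cohort.

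A reader might also count any prolonged stay as a route to a Grade II SAE, since under Table 9 the "inpatient period may be prolonged for subjects/patients in all dose levels in all cohorts", including "if the SRC considers it necessary for determining safety and tolerability for a future dose level cohort". That goes too far: limit II makes a stay an SAE only when a suspected adverse event is the reason. A stay requested by the SRC to inform a later cohort is not such a stay by itself.

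**Conclusion.** The point holds as a narrow gap in Table 6. One related Grade II SAE in Part A leads to no suspension: two non-suspending rows apply if it is reversible, none if it is not. In Part B the same event suspends the cohort until SRC review. The reading rests on the current protocol text and on a Grade II SAE being possible under its definitions.

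The practical effect is small. The event should be uncommon. Part A is single-dose, so the affected subject's own dosing cannot change. The rule matters only for Part A cohorts still to be dosed, which may be none. Nothing in the documents shows that any subject has been affected. The contrast with Table 8 applies only to serious events; in Part B a single non-serious, non-reversible Grade II event falls under the individual-patient rules of Table 7. This is a low-cost improvement, not a defect in the study's main safety oversight.

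**What to change.** Change Table 6 in three places:

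1. Relabel the existing Grade II rows as moderate, not serious, so that they do not overlap the new row.
2. Add a Grade II row for moderate, serious events: reversibility not applicable, one or more subjects, dose level and escalation suspended, ad hoc SRC review. Resumption at the same or a higher dose follows Section 4.7.3, that is, SRC review plus authority and IEC/IRB approval if local regulations require it. The SRC may allow a lower dose.
3. Give one non-serious, non-reversible Grade II case the existing escalation-hold action, so that it matches a row.

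Pointing the new row to Section 4.7.3 keeps it consistent with the general suspension text, which does not leave same-dose resumption to the SRC alone where approvals are required locally. Tables 7 and 8 need no change. A Grade I SAE would remain outside the new row.

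The cost is an edit to one table and, for each such event, a pause in dosing, an ad hoc SRC meeting and any locally required approvals. These should be rare.

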4.7.3.2. Individual Patient Progression/Escalation and Suspension/Stopping Rules in Part B

Individual progression/escalation and suspension/stopping rules applying only to individual patients enrolled in Part B are presented in [Table 7](#). If an individual patient meets a suspension/stopping rule, the SRC will meet to determine whether dosing of the remaining

patients in the cohort can continue. [Table 7](#) applies to AEs considered likely to be related to the underlying disease, or AEs considered possibly or definitely related to study drug.

CTCAE criteria will be used to grade AEs. For patients with abnormal renal function consistent with the underlying disease at baseline, evidenced by elevated serum creatinine, the change in this parameter from baseline should be used in grading AEs, rather than laboratory normal values.

Table 7: Individual Patient Progression/Escalation and Suspension/Stopping Rules for Part B

CTCAE Grade ^a	Severity/Seriousness	Action
I	Mild	No action required.
II	Moderate	Dose administration will be discontinued unless the AE is considered unrelated to study drug or reversible and continued dosing in the study is considered safe by the SRC.
III	Severe, not serious	
	Severe, serious	Dose administration will be discontinued.
IV/V	Life-threatening/Fatal	Dose administration will be discontinued.

Abbreviations: AEs=adverse events; SRC=Safety Review Committee.

^a Common Terminology Criteria for Adverse Events will be used to grade AEs.

4.7.3.3. Cohort Progression/Escalation and Suspension/Stopping Rules in Part B

Study cohort progression/escalation and suspension/stopping rules for AEs considered likely to be related to the underlying disease and for AEs considered possibly or definitely related to study drug for Part B are described in [Table 8](#). If a patient meets a stopping rule, the patient will be managed as clinically indicated and asked to complete all safety assessments according to the protocol. For patients with abnormal renal function consistent with their underlying disease at baseline, evidenced by elevated serum creatinine, the change in this parameter from baseline should be used in grading AEs, rather than laboratory normal values.

Table 8: Cohort Progression/Escalation and Suspension/Stopping Rules for Part B

Adverse Event(s)	Action
If ≥ 1 patient in a cohort experiences a severe AE and/or SAE, judged to be possibly or definitely related to study drug	Dosing within that cohort, and in any cohorts receiving a higher dose, will be suspended until SRC review. Following data review, the SRC may permit continuation of any ongoing Part B cohort. Any further dose escalation in a subsequent cohort will be suspended. Resumption of dose escalation will require a substantial amendment, approved by the regulatory authority and relevant ethics committee, if required by local regulations. However, de-escalation to a lower dose, or intermediate but lower dose, may be allowed by the SRC without a protocol amendment.
If ≥ 1 patient in Part B experiences a Grade 4 or 5 AE ^a judged to be possibly or definitely related to study drug	Dosing of all patients in Part B will be suspended until SRC review. Resumption of the study will require a substantial amendment, approved by the regulatory authority and relevant ethics committee, if required by local regulations.

Abbreviations: AE=adverse event; SAE=serious adverse event; SRC=Safety Review Committee.

a Common Terminology Criteria for Adverse Events will be used to grade AEs.

4.8. Adaptive Study Design Features

The use of adaptive study design features will allow for the continuing development of the study as new data emerge; therefore, the study can be adjusted in accordance with the prespecified areas, features, and limits listed in [Table 9](#).

Table 9: Adaptive Study Design Areas, Features, and Limits

Areas	Features	Limits
A. Dosing regimen	1. Dosing regimens may be determined or adapted in accordance with safety, tolerability, and available PD data collected up to the decision making time point. 2. The term “dosing regimen” includes: (1) the dose level administered, (2) the frequency of dosing, and (3) the duration of dosing, ie, number of doses administered. Accordingly, these can be adjusted individually or in combination.	I. The starting dose for subjects in Part A will be 0.3 mg/kg. II. The starting dose for subjects in Part B of the study will not exceed doses already evaluated and considered safe and tolerable in Part A. III. In Part A, provided no safety or tolerability concerns have occurred, the maximum single dose administered will be 6 mg/kg. IV. The interval between doses in Part B may be increased or decreased, but will not exceed 3 doses over a 57 day period.

Table 9: Adaptive Study Design Areas, Features, and Limits

Areas	Features	Limits
		
V. Duration of dosing: no more than 1 dose will be administered in Part A; dosing will not extend beyond 3 doses over a 57 day period in Part B.
 
VI. The maximum dose level in Part B will not exceed a dose found to be safe and well-tolerated in Part A.

B. Overlap	1. Dosing regimens may overlap.	I. Protocol-specific minimum study progression/escalation requirements for the SRC must be met before dose progression/escalation (Section 4.7).
C. Cohort Sizes	
1. Withdrawn subjects (Part A) and patients (Part B) can be replaced at the discretion of the Sponsor and Investigator if not withdrawn for safety reasons (Section 5.3).
 
2. Replacement subjects may be enrolled in an ongoing cohort, or dosed together as a group or separately.
	
I. Protocol-specific minimum requirements must be met before dose escalation (Section 4.7).
 
II. Provided suspension or stopping rules have not been met, the SRC may permit up to 2 cohorts in Part B to be extended by up to 4 additional patients per cohort receiving active treatment to further characterize the safety, tolerability, and PD of the study drug.

D. Optional Cohorts	1. Optional cohorts may be included to explore additional dosing regimens	
I. Up to 2 optional cohorts may be included in Part A.
 
II. Up to 3 optional cohorts may be included in Part B.
 
III. Cohort sizes will not exceed 8 subjects for each optional cohort in Part A, and 8 patients for each optional cohort in Part B.
 
IV. To further explore safety, tolerability, PD, and/or PK, study drug dose level may be escalated or de-escalated to a lower and/or to intermediate dose levels. Dose escalation in Part B will not exceed a dose level found to be safe and well-tolerated in Part A.
 
V. Dosing in optional cohorts will follow the same randomization list as that in planned cohorts in the respective parts of the study.
 
VI. The total number of study subjects/patients indicated in Section 4.3 cannot be exceeded.

E. Samples and assessments	1. If applicable, the inpatient period may be prolonged for subjects/patients in all dose levels in all cohorts if considered by the Investigator to be necessary for clinical reasons or for expeditious	
I. If applicable, a maximum extended inpatient period due to clinical concerns cannot be defined as the extension will be as long as necessary to ensure the safety of the subjects/patients.
 
II. If applicable, an unplanned or extended inpatient stay because of a suspected adverse

Table 9: Adaptive Study Design Areas, Features, and Limits

Areas	Features	Limits
	conduct of the study. Prolonged inpatient periods will be recommended on a subject/patient, case-by-case basis and/or if the SRC considers it necessary for determining safety and tolerability for a future dose level cohort.	event will constitute a serious adverse event and will be considered in the context of the study stopping rules (Section 4.7).
	2. Specialist referrals may be made if considered clinically necessary by the Investigator, delegate, Sponsor, or SRC for subjects/patients on a case-by-case basis.	I. Specialist referrals for subjects/patients will be determined on a case-by-case basis, as necessary to ensure the safety of subjects/patients, so a maximum number of referrals cannot be defined.
	3. In Part A and B, timing of PK and/or PD samples (blood and/or urine) may be adjusted in accordance with evolving data and dosing schedule/regimen. 4. In Part A and B, additional or fewer PK and/or PD samples (blood and/or urine) may be obtained in accordance with evolving data and dosing schedule.	I. Maximum blood volume for any subject/patient is based on age and weight guidelines; the maximum blood volume will not be exceeded. (Section 7). II. Optional PK and/or PD analysis can be performed at any stage during or after the study to facilitate decision-making and/or to increase understanding of the compound (ie, samples will be obtained, but not necessarily analyzed; applicable to Features 3 and 4). III. The optional analysis is limited to the protocol-specified purpose (applicable to Features 3 and 4).
Abbreviations: PD=pharmacokinetic; PK=pharmacokinetic; SRC=Safety Review Committee.		

5. SELECTION AND WITHDRAWAL OF PATIENTS

5.1. Inclusion Criteria

Each subject/patient must meet all of the following inclusion criteria to be eligible for enrollment in the study.

5.1.1. Inclusion Criteria for Parts A and B

1. Male and female subjects aged 18 to 64 years (or age of legal consent, whichever is older), inclusive (Part A) and 6 to 64 years, inclusive (Part B).
2. Women of child-bearing potential must have a negative pregnancy test, cannot be breast feeding, and must be willing to use a highly effective method of contraception 14 days before first dose, throughout study participation until the completion of the follow-up periods (see [Section 6.4](#)).

3. Willing to comply with protocol-required visit schedule and visit requirements; and able to provide written informed consent and assent in the case of patients under the age of legal consent.

5.1.2. Additional Inclusion Criteria for Part A

4. Body Mass Index (BMI) of 18-30 kg/m², inclusive at screening and Day -1.

5.1.3. Additional Inclusion Criteria for Part B

5. Documentation or confirmation of PH1 as determined by genetic analysis and biochemical criteria and definite diagnosis based on the presence of AGXT mutations or reduced hepatic AGT enzyme activity that is considered evidence of the disease state (medical history)
6. 24-hour urinary oxalate excretion of >0.7 mmol/1.73m²/day
7. Estimated GFR of >45 mL/min/1.73m² (calculation will be based on the MDRD formula for patients ≥18 years of age and the Schwartz Bedside Formula for patients <18 years of age; Section 11.2 in the Appendix)
8. If taking Vitamin B6 (pyridoxine), must have been on stable regimen for at least 90 days before study entry, and willing to remain on this stable regimen for the study duration.

